6.10. Clinical Laboratory Assessments

Blood and urine samples will be collected throughout the study as outlined below and in [Appendix 2](#) and [Appendix 3](#).

6.10.1. Blood Samples

Blood samples will be collected at all study visits (including the open-label rollover extension phase), unless otherwise noted for the below noted laboratory analyses:

- Serum pregnancy test at the Screening Visit (females of childbearing potential only). If the test is positive, the subject will not be enrolled. At all subsequent study visits, serum pregnancy test will be performed if urine pregnancy test is positive.

- Chemistry profile: alkaline phosphatase, AST, ALT, GGT, total bilirubin, direct and indirect bilirubin, total protein, albumin, bicarbonate, BUN, calcium, chloride, creatinine, glucose, phosphorus, magnesium, potassium, sodium, uric acid, amylase (reflex lipase testing is performed in subjects with total amylase $> 1.5 \times$ ULN)
 - At Day 1, Weeks 24, 48, 72, 96, every 24 weeks after Week 96, End of Blinded Treatment Visit, and every 24 weeks after the End of Blinded Treatment Visit in the open label extension phase glucose will be done as part of the fasting metabolic assessments and not part of the chemistry profile.
 - PT/INR (prothrombin time/international normalized ratio) will be analyzed at Screening and Day 1 Visits.
- Metabolic assessments: Fasting (no food or drinks, except water, at least 8 hours prior to blood collection) glucose and lipid panel (total cholesterol, HDL, direct LDL, and triglycerides) at Day 1, Weeks 24, 48, 72, 96, every 24 weeks after Week 96, End of Blinded Treatment Visit, and every 24 weeks after End of Blinded Treatment Visit in the open label rollover extension phase. If the subject has not fasted prior to the visit, the visit may proceed, but the subject must return within 72 hours in a fasted state to draw blood for the metabolic assessments.
- Estimated glomerular filtration rate according to the Cockcroft-Gault formula
 - If eGFR is < 50 mL/min at Day 1 visit, Cystatin C will be measured
- Hematology profile: complete blood count (CBC) with differential and platelet count
- CD4+ cell count and CD4%
- Plasma HIV-1 RNA
- Hepatitis B Virus (HBV) blood panel:
 - HBV serologies: HBsAg, reflex anti-HBs Ab, HBeAg, reflex anti-HBe Ab
(Screening, Day 1 and Weeks 12, 24, 36, 48, 60, 72, 84, 96 and every 24 weeks after Week 96 until the End of Blinded Treatment Visit. In the open-label extension phase, testing will be completed every 48 weeks)
- Plasma HBV DNA will be monitored at all study visits.
- Plasma sample for HBV Genotyping (A-H) at Day 1 visit.
- Serum samples for potential sequence analysis of HBV polymerase/reverse transcriptase (pol/RT) should be collected at all time points except screening. Sequencing analysis of the HBV pol/RT will be attempted for all subjects who remain viremic (HBV DNA ≥ 69 IU/mL) at Weeks 48, 96 and Early Study Drug Discontinuation Visit as early as Week 8 and according to Section 6.15.

- Hepatitis C virus (HCVAb) serology at Screening, Weeks 48, 96, every 48 weeks after Week 96 and every 48 weeks in the open label rollover extension phase. Subjects who are HCVAb positive will have a HCV RNA test performed.
- HIV-1 genotype testing (protease and reverse transcriptase) at the Screening Visit. The HIV-1 PR/RT genotype testing may not be performed for subjects that fail to meet other screening criteria.
- Sample collection for resistance testing for subjects who meet the criteria for HIV-1 virologic failure will be managed according to the Management of Virologic Rebound Section 6.14.
- Trough PK blood sample will be obtained 20-28 hours following the last dose at Weeks 4, 12, and 36.
 - Subject must be instructed to not take their study drugs on the morning of their visit for the trough sample collection. If the subject has taken their dose of study drugs prior to the visit, the visit may proceed, but the subject must return within 72 hours for the trough PK sample collection.
- Following an observed dose, one post-dose PK blood sample will be collected between 1 and 4 hours post-dose at Weeks 8 and 24.
 - In the event a subject routinely takes their study drug in the evening, the subject will not be instructed to change their dosing time, or participate in the observed dose. A single PK sample will be collected at Weeks 8 and 24. Time of sample collection will be recorded in the source documents and the subject will be asked to confirm the time of the last dose, which will also be recorded in the source documents.
- Plasma and serum storage sample for safety, virology, or PK testing (not collected at Screening and 30 Day Follow-up Visits)
- Whole blood storage sample for safety, virology, or PK testing at Day 1, Week 48 and Week 96. This sample is not optional.

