1.6. Risk/Benefit Assessment for the Study

HIV and HBV co-infection worsens morbidity and mortality synergistically; co-infected patients have higher risk of cirrhosis and hepatocellular carcinoma. In HIV-positive patients co-infected with HBV, F/TDF or F/TAF are the preferred NRTI backbone of a fully suppressive antiretroviral regimen {[Panel on Antiretroviral Guidelines for Adults and Adolescents 2016](#)}. This study seeks to generate safety and efficacy data of B/F/TAF FDC in this population by enrolling treatment naïve patients. The comparator regimen contains DTG and F/TDF, a fully suppressive regimen. Potential risks associated with all classes of ARVs include immune reconstitution syndrome, lipodystrophy, and lactic acidosis with steatosis. The risk of class effects is considered to be low. Potential benefits may include provision of a new ARV therapy to patient population that may have fewer side effects than alternative therapies. Other potential benefits include provisions of fixed dose combination therapy, and the knowledge that patient participation will contribute to the body of knowledge of HIV therapies.

In summary, the risk/benefit for this study is acceptable due to the following considerations:

- Treatment of HBV is indicated and important in all HIV co-infected patients due to accelerated progression of liver disease
- TDF and TAF are approved for the treatment of HBV infection
- B/F/TAF has been proven to be safe, well tolerated and effective in the treatment of HIV-infected patients
- Hepatic flares, defined by an increase in ALT of five-fold above upper limit of normal, are not uncommon early in treatment initiation and will be closely monitored (refer to Section [7.5.4](#))
- Risk of nephrotoxicity, defined as a decreased in eGFR < 50ml/min is considered to be low and will be closely monitored (refer to Section [7.5.5](#))

The benefit-risk assessment for this study is favorable at this time.

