4.2. Inclusion Criteria

Subjects must meet **all** of the following inclusion criteria to be eligible for participation in this study.

- 1) The ability to understand and sign a written informed consent form, which must be obtained prior to initiation of study procedures
- 2) Age \geq 18 years
- 3) HIV-1 co-infection:
 - a) Must be HIV antiretroviral treatment naive with plasma HIV-1 RNA \geq 500 copies/mL at screening
 - b) \leq 10 days of prior therapy with any antiretroviral agent, including lamivudine and entecavir, following a diagnosis of HIV-1 infection (except the use for PrEP or PEP, up to one month prior to screening)
 - c) Screening genotype report must show sensitivity to FTC and TFV. This report will be provided by Gilead Sciences. Alternatively, if genotype results from a local laboratory obtained \leq 90 days prior to screening visit date show sensitivity to these drugs, this genotype will be acceptable to fulfill this inclusion criterion in the event that the genotype obtained at screening is not yet available and all other inclusion/exclusion criteria have been confirmed
- 4) HBV co-infection:
 - a) Must be HBV treatment naïve (defined as $<$ 12 weeks of oral antiviral treatment)
 - b) Screening HBV DNA \geq 2000 IU/mL
- 5) Normal ECG (or if abnormal, determined by the investigator not to be clinically significant)

- 6) Estimated glomerular filtration rate (eGFR) ≥ 50 mL/min according to the Cockcroft-Gault (C-G) formula {[Cockcroft 1976](#)}:

Male:
$$\frac{(140 - \text{age in years}) \times (\text{wt in kg})}{72 \times (\text{serum creatinine in mg/dL})} = \text{CLcr (mL/min)}$$

$$\frac{(140 - \text{age in years}) \times (\text{wt in kg})}{72 \times (\text{serum creatinine in umol/L}) \times 0.6786} = \text{CLcr (mL/sec)}$$

Female:
$$\frac{(140 - \text{age in years}) \times (\text{wt in kg}) \times 0.85}{72 \times (\text{serum creatinine in mg/dL})} = \text{CLcr (mL/min)}$$

$$\frac{(140 - \text{age in years}) \times (\text{wt in kg}) \times 0.85}{72 \times (\text{serum creatinine in umol/L}) \times 0.6786} = \text{CLcr (mL/sec)}$$

- 7) Hepatic transaminases (AST and ALT) $\leq 10 \times$ upper limit of normal (ULN)
- 8) Total bilirubin $\leq 2.5 \times$ upper limit of normal (ULN)
- 9) Adequate hematologic function (absolute neutrophil count $\geq 750/\text{mm}^3$ (≥ 0.75 GI/L); platelets $\geq 50,000/\text{mm}^3$ (≥ 50 GI/L); hemoglobin ≥ 8.5 g/dL (≥ 85 g/L))

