6.2. Pretreatment Assessments

6.2.1. Screening Visit

Subjects will be screened within 30-days before Day 1 to determine eligibility for participation in the study. The following will be performed and documented at screening:

- Obtain written informed consent
- Obtain medical history including history of HIV-1 disease-related events and prior medications within 30 days of the screening visit
- Complete physical examination (urogenital/anorectal exams will be performed at the discretion of the Investigator)
- 12-lead ECG performed supine
- Height
- Vital signs measurement (blood pressure, pulse, respiration rate, and temperature), including weight
- Obtain blood and urine samples as described in Section [6.10](#)
- Review of adverse events and concomitant medications

Subjects meeting all of the inclusion criteria and none of the exclusion criteria will return to the clinic within 30-days after screening for the Day 1 Visit.

From the time of obtaining informed consent through the first administration of investigational medicinal product, record all serious adverse events (SAEs), as well as any adverse events related to protocol-mandated procedures on the adverse events electronic case report form

(eCRF). All other untoward medical occurrences observed during the screening period, including exacerbation or changes in medical history are to be captured on the medical history eCRF (Section 7).

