6.10.3. Blood Storage Samples

Any residual blood samples from the samples collected will be frozen and stored. These stored blood samples may be used by the Sponsor or its research partners for HIV-1 and/or HBV or related diseases, genotyping/phenotyping assays or their development, for retesting the amount of HIV-1 and/or HBV in the blood, for measurement of antiviral drug levels in the blood, or for testing to learn more about how the study drug has worked against HIV-1 and/or HBV or related diseases, or clinical laboratory testing to provide additional safety data. No human genetic testing will be performed without expressed consent of study subjects. At the conclusion of this study, these samples may be retained in storage by Gilead Sciences for a period up to 15 years.

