7.5.5. Management of Potential Nephrotoxicity

Estimated glomerular filtration rate (eGFR), according to the Cockcroft-Gault formula for creatinine clearance, will be followed post-baseline during the study. All subjects with estimated eGFR < 50 mL/min must have serum creatinine measured again within 3 calendar days of receipt of results.

At the time of this repeat serum creatinine assessment, Cystatin C will also be measured and the eGFR by CKD-EPI (cystatin C) will be calculated and compared with the baseline measurement.

Any subjects who have an eGFR < 50 mL/min that also experience > 20% reduction in eGFR by CKD-EPI (cystatin C) from baseline or who have other clinical and/or laboratory evidence of acute renal failure will be discussed with the Medical Monitor and potentially discontinue from study drugs.

For subjects with eGFR < 50 mL/min who are not discontinued based on toxicity management procedures above and considered to have stable renal function per Principal Investigator and Medical Monitor, it is not mandatory to repeat eGFR assessments within 3 days.

CKD-EPI (cystatin C) formula adjusted for age and sex:

$$\text{eGFR (mL/min/1.73m}^2\text{)} = 133 \times \min(\text{Scys}/0.8, 1)^{-0.499} \times \max(\text{Scys}/0.8, 1)^{-1.328} \times 0.996^{\text{Age}} [\times 0.932 \text{ if female}]$$

Where Scys is serum cystatin C (mg/L), min (Scys/0.8,1) indicates the minimum of Scys/0.8 or 1, and max (Scys/0.8,1) indicates the maximum of Scys/0.8 or 1.

Once an individual subject has developed any of these renal changes and followed the management guidelines above, it is not necessary to have repeat evaluations if it is determined that it is safe for that subject to continue on treatment with standard follow-up visits as described in the protocol.

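### The > 20% cystatin-C eGFR criterion has no scheduled baseline for the participants it is meant to cover

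*Protocol*

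**What the plan says.** - **Entry.** Protocol Section 4.2 requires eGFR of at least "50 mL/min according to the Cockcroft-Gault (C-G) formula". Section 6.2.1 sets the timing: "Subjects will be screened within 30-days before Day 1".
- **Day 1.** Section 6.10.1: "If eGFR is < 50 mL/min at Day 1 visit, Cystatin C will be measured". Cystatin C is not in the chemistry profile, and Appendices 2 and 3 do not schedule it. The SAP does not mention it; its renal summaries (Section 7.2.6) use serum creatinine and Cockcroft-Gault eGFR.
- **On study.** Under Section 7.5.5, a post-baseline Cockcroft-Gault eGFR below 50 mL/min leads to a repeat creatinine within 3 days of the result. Cystatin C is measured at the same time, and "the eGFR by CKD-EPI (cystatin C) will be calculated and compared with the baseline measurement".
- **Action.** A participant below 50 with more than a "20% reduction in eGFR by CKD-EPI (cystatin C) from baseline", or with other evidence of acute renal failure, is discussed with the Medical Monitor and may stop study drug.
- **Stored blood.** Section 6.10.1 also collects a "Plasma and serum storage sample for safety, virology, or PK testing" at every visit except Screening and the 30-Day Follow-Up, so Day 1 is included. Section 6.10.3 allows, but does not require, stored blood to be used for "clinical laboratory testing to provide additional safety data".

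**The concern.** The rule for drawing the baseline and the rule that uses it select nearly disjoint groups. Section 7.5.5 is aimed at someone who enters with adequate renal function and loses it on treatment. Section 6.10.1 draws baseline cystatin C only in someone who passed the threshold at screening and was already below it at Day 1.

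The protocol leans on this section. Section 1.6 says that the nephrotoxicity risk "is considered to be low and will be closely monitored" and refers the reader to Section 7.5.5. Within that section, the > 20% limb is the only one with a numerical threshold for a fall.

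A cystatin-C check is also useful here in particular. Section 1.2.3.1 attributes creatinine rises on bictegravir to presumed OCT2 inhibition, and the Phase 2 summary reports falls in Cockcroft-Gault eGFR on both bictegravir and dolutegravir. A creatinine-based value below 50 may therefore partly reflect altered creatinine handling. Separating that from a true decline is presumably why the cystatin-C step exists, though the protocol does not say so. Without a baseline, the step loses its measure of change.

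**Working it through.** The plan states no figure on this point, so there is none to reproduce. The check has three parts.

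**1. Who has a baseline?**

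| Cockcroft-Gault eGFR at Day 1 | Cystatin C at Day 1 | If eGFR is later < 50 |
|---|---|---|
| < 50 (despite ≥ 50 at screening) | Yes (6.10.1) | > 20% fall can be computed |
| ≥ 50 | Not scheduled | > 20% fall cannot be computed |

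To gauge how lopsided this is, a simulation assumed:
- lognormal eGFR with the Phase 2 spread (log-SD 0.245) and a median of 125.3, 110 or 95 mL/min;
- within-person CV of 5% to 12%;
- a mean on-treatment log-change of -0.08 (SD 0.15) over ten later visits.

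The chance of Day 1 eGFR < 50 given screening ≥ 50 was 0.004% to 0.31%, or about 0.01 to 0.75 of the 243 treated (SAP Appendix 3). Of those with any later value below 50, 97% to 99% had Day 1 eGFR ≥ 50 and so no scheduled baseline. Only the Phase 2 median and spread come from the documents; the rest is assumed.

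**2. Can the on-study value settle the criterion alone?** With cystatin C above 0.8 mg/L at both times, the age and sex terms of the Section 7.5.5 formula essentially cancel:

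fall = 1 − (Scys at baseline / Scys on study)^1.328

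For a 40-year-old man with on-study cystatin C of 1.4 mg/L, eGFR = 133 × (1.4/0.8)^-1.328 × 0.996^40 = 53.9 mL/min/1.73 m².

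| Baseline cystatin C (mg/L) | Baseline eGFR | Fall |
|---|---|---|
| 1.0 | 84.2 | 36.0% |
| 1.18 | 67.6 | 20.3% |
| 1.3 | 59.5 | 9.4% |
| 1.4 | 53.9 | 0.0% |

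The same on-study result can lie on either side of 20%. The Cockcroft-Gault baseline cannot stand in, because it is a different estimator in different units (mL/min).

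**3. How many would need the baseline?** This is illustrative. Phase 2 baseline eGFR was 125.3 (105.7, 147.0) mL/min (Section 1.2.3.3). Week 48 changes were -7.0 (-18.7, 1.6) on B+F/TAF and -11.3 (-24.5, -0.8) on DTG+F/TAF. With SD = interquartile range / 1.349:
- baseline: 41.3 / 1.349 = 30.6
- change: 20.3 / 1.349 = 15.0 and 23.7 / 1.349 = 17.6

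Take a normal baseline truncated at 50, with 120 per arm. The median-shift count is 120 × P(50 to 57) + 120 × P(50 to 61.3). The second count adds the spread of change at one visit, independent of baseline.

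| Median entry eGFR | Median shift only | With spread of change |
|---|---|---|
| 125.3 (Phase 2) | 2.1 | 5.5 |
| 105 (assumed) | 7.8 | 15.5 |
| 90 (assumed) | 16.4 | 27.4 |

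The entries are participants of 240 below 50 mL/min. A lognormal baseline with the Phase 2 quartile spread and median 125.3 gives 0.3 and 3.0 in place of 2.1 and 5.5. If the change also scales with baseline, 3.0 becomes 0.6.

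**The case against.** The strongest reply is that this is a missing cross-reference and the criterion still works. Day 1 plasma and serum are held, safety testing on them is permitted, and Section 7.5.5 tells the site to compare with baseline; only a sentence joining these is absent. The consequence is also soft: the > 20% limb leads to a Medical Monitor discussion and possible discontinuation, so it is not a stopping rule. Much else still operates: Cockcroft-Gault eGFR at every visit, repeat creatinine, the acute-renal-failure limb, fasting urine renal markers with a Day 1 value (Section 6.10.2), and withholding or stopping drug for confirmed, clinically significant, drug-related Grade 3 or 4 creatinine (Sections 7.5.2 and 7.5.3). Finally, the normal model exaggerates the left tail, and the 105 and 90 medians have no source.

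Most of this stands as a limit on the consequences. The gap is repairable, the other safeguards are real, and the lower counts are as defensible as the higher ones.

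It does not remove the gap. Use of stored blood is optional, and nothing tells a site or the laboratory to run cystatin C on it. The protocol does give that kind of instruction when it intends it: Section 6.15 directs sequencing of the Day 1 sample for HBV resistance. The creatinine grades act far later (Grade 3 starts above 3.00 mg/dL in Appendix 5) and do not replace an early check on relative fall. The inconsistency also does not depend on the count.

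**Conclusion.** The concern holds. As written, the > 20% criterion in Section 7.5.5 has no scheduled baseline for any participant with Day 1 eGFR of 50 mL/min or more. Under the simulation assumptions, that is 97% to 99% of those who later fall below 50. This conclusion rests on the text alone.

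The number of people involved is uncertain and probably small. With the Phase 2 median it is about 0 to 6 of 240 at a single visit; it reaches 8 to 27 only under assumed lower entry medians. The Phase 2 comparator was DTG+F/TAF, whereas this trial uses DTG+F/TDF, so these counts may not carry over.

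The effect is confined to safety management. The primary and co-primary analyses, alpha, power and the SAP renal summaries are unchanged. It should be corrected because a numerical safety criterion that cannot be computed gives less protection than the protocol claims.

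**What to change.** Add to Sections 6.10.1 and 7.5.5: if on-study eGFR is < 50 mL/min, cystatin C will be assayed on the participant's stored Day 1 serum, and that result is the baseline for the > 20% comparison. First confirm with the central laboratory that stored serum is suitable for the assay. If it is not, measure cystatin C at Day 1 in every participant.

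The first option costs one sentence in two sections and an assay only for those who fall below 50: up to about 27 of 240 at one visit on the assumptions above, and probably far fewer. The second costs one added Day 1 assay per participant. Neither changes visits, endpoints, sample size or the analysis.

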6.15. HBV Resistance Surveillance

Sequencing analysis of the HBV pol/RT will be attempted for all subjects who remain viremic (HBV DNA ≥ 69 IU/mL) at Weeks 48 and 96 (or Early Study Drug Discontinuation Visit as early as Week 8), and for those with virologic breakthrough defined as:

- Two consecutive HBV DNA values ≥ 69 IU/mL after achieving < 69 IU/mL, or
- Two consecutive ≥ 1.0 Log₁₀ increases in HBV DNA from nadir for those who did not achieve a result < 69 IU/mL

Sequencing of the corresponding Day 1 sample will also be conducted for any subject who remains viremic or experiences virologic breakthrough. As it may not be known at the time of the visit whether a patient is viremic or if it will be their last study visit, a separate virology sample for potential resistance surveillance will be collected at each study visit. Phenotypic analysis will be performed for adherent subjects that are subjected to sequence analysis.

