Appendix 2. Study Procedures Table (Blinded Phase)

Study Procedures	Screening ^a	Day 1 ^b	End of Week ^{e, q}										Post-Week 96 ^{e, r}	End of Blinded Treatment Visit	30-Day Follow- up ^p	Early Study Drugs DC ^c	
			4	8	12	24	36	48	60	72	84	96	Every 12 Weeks				
Informed Consent	X																
Medical History	X																
Concomitant Medications	X	X	X	X	X	X	X	X	X	X	X	X	X	X	X	X	X
Adverse Events	X	X	X	X	X	X	X	X	X	X	X	X	X	X	X	X ^f	X ^f
Complete /Symptom-Directed Physical Exam	X	X	X ^d	X ^d	X ^d	X	X ^d	X	X ^d	X ^d	X ^d	X	X ^d	X	X ^{d,f}	X^f	X^f
12-Lead ECG (performed supine)	X																
Height	X																
Vital signs (blood pressure, pulse, respiration rate, and temperature), and Weight	X	X	X	X	X	X	X	X	X	X	X	X	X	X	X	X	X
Urinalysis	X	X	X	X	X	X	X	X	X	X	X	X	X	X	X	X ^f	X ^f
Urine Sample for Markers of Renal Dysfunction		X				X		X				X					X
Pregnancy Test ^g	X	X	X	X	X	X	X	X	X	X	X	X	X	X	X		X
Chemistry Profile ^h	X	X	X	X	X	X	X	X	X	X	X	X	X	X	X	X ^f	X ^f
Metabolic Assessments ⁱ		X				X		X		X		X	X ⁱ	X			

Study Procedures	Screening ^a	Day 1 ^b	End of Week ^{e, q}										Post-Week 96 ^{e, r}	End of Blinded Treatment Visit	30-Day Follow- up ^p	Early Study Drugs DC ^c	
			4	8	12	24	36	48	60	72	84	96	Every 12 Weeks				
Estimated Glomerular Filtration Rate	X	X	X	X	X	X	X	X	X	X	X	X	X	X	X	X ^f	X
Hematology Profile ^j	X	X	X	X	X	X	X	X	X	X	X	X	X	X	X	X ^f	X ^f
Plasma HIV-1 RNA	X	X	X	X	X	X	X	X	X	X	X	X	X	X	X	X	X
CD4+ Cell Count and CD4%	X	X	X	X	X	X	X	X	X	X	X	X	X	X ⁿ	X	X	X
Blood Storage Samples ^o		X	X	X	X	X	X	X	X	X	X	X	X	X	X		X
HCV Serology ^u	X							X					X	X			
HIV-1 Genotype ^k	X																
HIV-1 Genotype/Phenotype ^c								X ^c					X ^c				X ^c
HBV Blood panel ^t	X	X			X	X	X	X	X	X	X	X	X	X ^t			
HBV Genotyping (A-H)		X															
Plasma HBV DNA	X	X	X	X	X	X	X	X	X	X	X	X	X	X	X	X	X
Serum sample HBV Resistance Surveillance ^w		X	X	X	X	X	X	X ^w	X	X	X	X	X	X ^w	X	X	X ^w
Trough PK Blood Sample ^l			X		X		X										
Post-Dose PK Blood Sample ^m				X		X											

Study Procedures	Screening ^a	Day 1 ^b	End of Week ^{e, q}										Post-Week 96 ^{e, r}	End of Blinded Treatment Visit	30-Day Follow- up ^p	Early Study Drugs DC ^c	
			4	8	12	24	36	48	60	72	84	96	Every 12 Weeks				
CCI																	
Randomization ^v		X															
Provide subject dosing diary to subjects		X	X	X	X	X											
Study Drug Dispensation		X ^b	X	X	X	X	X	X	X	X	X	X	X	X	X ^s		
Study Drug Accountability			X	X	X	X	X	X	X	X	X	X	X	X	X		X

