Appendix 3. Study Procedures Table (Open Label Rollover Extension)

Study Procedures	Post End of Blinded Treatment Visit (every 12 weeks)^{a,e,l}	30-Day Follow-up^k	Early Study Drugs DC^c
Adverse Events	X	X ^f	X ^f
Concomitant Medications	X	X	X
Complete /Symptom-Directed Physical Exam	X ^d	X ^{d,f}	X^f
Vital signs (blood pressure, pulse, respiration rate, and temperature) and Weight	X	X	X
Urinalysis	X	X ^f	X ^f
Urine Pregnancy Test ^g	X		X
Chemistry Profile ^h	X	X ^f	X ^f
Metabolic Assessments ⁱ	X		
Estimated Glomerular Filtration Rate	X	X ^f	X
Hematology Profile ^j	X	X ^f	X ^f
Plasma HIV-1 RNA	X	X	X
CD4+ Cell Count and CD4%	X	X	X
Blood Storage Sample ^o	X		X
HBV Blood Panel ^m	X ^m		
Plasma HBV DNA	X		
HCV Serology ⁿ	X ⁿ		
HIV-1 Genotype/Phenotype ^e			X ^e
Study Drug Dispensation ^b	X		
Study Drug Accountability	X		X

a. Once the last subject completes the Week 96 visit and Gilead completes the Week 96 analysis, all subjects will return to the clinic (within 30 days ± 6 days) for an End of Blinded Treatment Visit. At the End of Blinded Treatment Visit, if safety and efficacy of B/F/TAF FDC is demonstrated for the HIV-1 and HBV coinfecting subjects following review of unblinded data, subjects in a country where B/F/TAF FDC is not available, will be given the option to receive B/F/TAF FDC in an open label extension phase until the product becomes accessible to subjects through an access program, or until Gilead Sciences elects to discontinue the study in that country, whichever occurs first.

- b. Open label study drug, B/F/TAF FDC will be dispensed to subjects participating in the Open-Label Rollover extension.
- c. Subjects who discontinue study drug during the open label rollover extension portion of the study will be asked to return to the clinic within 72 hours of stopping study drugs for the Early Study Drugs Discontinuation Visit followed by a 30-Day Follow-Up Visit. The subject will not continue attending the scheduled study visits.
- d. Symptom-directed physical examination as needed.

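### The extension schedule (Appendix 3) omits HBV DNA at both stopping visits and the HBV resistance sample throughout, although Sections 6.10.1 and 6.15 require both.

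*Protocol*

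**What the plan says.** The text of the protocol is consistent on this point:

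- Section 6.10 makes both its own text and the appendices operative: "Blood and urine samples will be collected throughout the study as outlined below and in" Appendices 2 and 3. It gives no order of precedence.
- Section 6.10.1 sets its scope as "Blood samples will be collected at all study visits (including the open-label rollover extension phase), unless otherwise noted".
- Its HBV DNA bullet reads "Plasma HBV DNA will be monitored at all study visits" and attaches no exception.
- For resistance, Section 6.10.1 says "Serum samples for potential sequence analysis of HBV polymerase/reverse transcriptase (pol/RT) should be collected at all time points except screening". It names viremia (HBV DNA of 69 IU/mL or more) as the trigger for sequencing "at Weeks 48, 96 and Early Study Drug Discontinuation Visit as early as Week 8".
- Section 6.15 adds that "a separate virology sample for potential resistance surveillance will be collected at each study visit".
- Sections 6.8.1 and 6.8.2 create an early discontinuation visit and a 30-day follow-up visit for extension participants. Both send the site to Section 6.10 for blood sampling.

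Appendix 3 departs from this. Its row "Plasma HBV DNA" is marked in the 12-weekly column and blank in the other two. It has no row corresponding to "Serum sample HBV Resistance Surveillance", which is a row of Appendix 2. SAP Appendix Table 2 reproduces the same blanks and the same missing row.

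**The concern.** Every participant has hepatitis B, and the study regimen treats it. Stopping that regimen carries a risk of HBV exacerbation, which the protocol recognises in Section 7.5.4.2. Section 6.8.2 says that extension participants who stop early do not continue scheduled visits after the 30-day follow-up. If a site schedules from Appendix 3, these participants have no planned HBV DNA at or after stopping. A viral rebound that precedes an ALT rise could go unseen.

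The discontinuation visit is also a named sequencing time point. Under the table, both the value that would trigger sequencing and the dedicated sample to sequence are missing.

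The safety issue applies mainly to early discontinuers and to completers who do not move to other HBV therapy. Completers may pass to access-program drug.

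**Working it through.** The main check compares documents; no figure of the plan is in dispute.

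**Text against tables**

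| Item and visit | Sections 6.10.1 / 6.15 | Appendix 3 | Appendix 2 (blinded phase) |
|---|---|---|---|
| HBV DNA, 12-weekly visits | required | marked | marked |
| HBV DNA, early discontinuation | required | blank | marked |
| HBV DNA, 30-day follow-up | required | blank | marked |
| HBV resistance serum, 12-weekly visits | required | no row | marked |
| HBV resistance serum, early discontinuation | required | no row | marked |
| HBV resistance serum, 30-day follow-up | required | no row | marked |
| HIV-1 RNA, both stopping visits | required | marked | marked |

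Appendix 3 therefore marks HBV DNA in 1 of 3 columns and the resistance sample in 0 of 3, where the text requires 3 of 3 for each.

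Three things rule out an innocent explanation:

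- The SAP copy shows the same pattern, so this is not a text-extraction fault.
- No Appendix 3 footnote explains the blanks.
- Section 6.10.1 writes its exceptions into the bullet concerned. HBV and HCV serology are every 48 weeks in the extension, and storage samples are not drawn at the 30-day visit. The HBV DNA and resistance bullets carry no extension exception.

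**Age of the last scheduled HBV DNA under Appendix 3**

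Inputs: extension visits every 12 weeks, or 84 days (Section 6.7); discontinuation visit within 72 hours, or 3 days, of stopping (Section 6.8.1); follow-up 30 days after that visit, with a window of 6 days either way (Section 6.8.2); 12-weekly visit window of 6 days either way after Week 12 OL (Section 6.7). The site is assumed to follow the table and to draw no unscheduled HBV DNA.

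Let t be the days from the last 12-weekly visit to stopping, from 0 to 84. With the discontinuation visit at its 72-hour limit, the age is t at stopping, t + 3 at the discontinuation visit and t + 3 + 30 = t + 33 at the 30-day visit.

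| Case | At stopping | Discontinuation visit | 30-day visit |
|---|---|---|---|
| Minimum, t = 0 | 0 | 3 | 33 |
| Average, t uniform on 0 to 84 (assumption) | 42 | 45 | 75 |
| Nominal maximum, t = 84 | 84 | 87 | 117 |
| All windows at their limits | 84 + 12 = 96 | 96 + 3 = 99 | 99 + 36 = 135 |

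If the discontinuation visit falls on the day of stopping, the nominal range at the 30-day visit is 30 to 114 days. For a completer whose dosing ends at the last 12-weekly visit (assumption), the value is 30 days old at follow-up, or 36 with the window.

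**The case against.** The best defence is that nothing in Appendix 3 forbids the samples. Sections 6.8.1 and 6.8.2 direct sites to Section 6.10, which joins its text and the appendices, so a site following both would collect everything. On that reading this is an incomplete summary table. The reading is reasonable, but it does not remove the conflict. Appendix 3 is itself a named source of instructions, and the text does not say that a blank cell should be ignored.

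The mitigations are real but partial:

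- ALT is scheduled at both stopping visits. Under Section 7.5.4.2, a confirmed rise (above 2 × Day 1 and above 10 × ULN) in a participant on no HBV therapy leads to reflex HBV DNA. Rebound before or without such a rise triggers nothing.
- Plasma and serum storage samples are taken at the 12-weekly and discontinuation visits and may serve virology. Section 6.15 nevertheless asks for a separate sample, and no storage sample is drawn at 30 days.
- Retesting residual blood for HBV is allowed by Section 6.10.3 but is discretionary.

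Some limits stand. The protocol sets no off-treatment action threshold for HBV DNA alone. The 30-day visit is not a named sequencing time point, so the resistance sample matters less there than the HBV DNA value. The ages above are calendar arithmetic and do not measure harm; the 135-day figure needs every window at its limit.

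**Conclusion.** The concern holds. The protocol text and its extension schedule disagree on HBV DNA at two visits and on the resistance sample at all extension visits, and the disagreement is unexplained.

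For an early discontinuer at a site following the table, the last scheduled HBV DNA would be 0 to 84 days old at stopping and 33 to 117 days old at the 30-day visit on nominal dates. The documents do not say how many participants entered the extension or stopped early in it, so the total effect cannot be sized.

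The consequence is confined to extension safety monitoring and resistance surveillance. Week 48 and Week 96 endpoints are unaffected, and on-treatment breakthrough can still be judged from the 12-weekly values. SAP Section 6.3.2.3 uses HBV DNA only up to 1 day after stopping. A 30-day value would be excluded, while a discontinuation-visit value drawn within that day could enter the descriptive missing = excluded summary. This should be corrected, but it does not threaten the trial's main conclusions.

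**What to change.** In Appendix 3, mark plasma HBV DNA under both 30-Day Follow-up and Early Study Drugs DC, and add the HBV resistance serum row as in Appendix 2. Align SAP Appendix Table 2 for consistency; no analysis method changes. If the sponsor meant to omit these samples, write the exception into Sections 6.10.1 and 6.15 instead, so that one instruction remains.

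The drafting cost is two marks and one row. The operating cost is one HBV DNA assay at each stopping visit and one serum tube at each extension visit. The text already requires all of these, and blood is already drawn at those visits for HIV-1 RNA and chemistry. As a protocol modification it needs IRB/IEC approval (Section 9.2.1).

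The SAP for the final analysis was signed in April 2024. If extension visits have ended, the useful step is to establish which instruction sites followed, state in the study report which stopping-visit HBV samples are missing, and consider testing stored or residual blood under Section 6.10.3.
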